6.2.1.3 Dose modification for other reasons

Eltrombopag dosing is to be temporarily discontinued in patients unable to ingest the drug due to mucositis or permanent vomiting.

6.2.2 Follow-up for toxicities

Patients whose treatment is interrupted or permanently discontinued due to an adverse event or clinically significant laboratory value must be followed up at least once a week (or more frequently if required by institutional practices, or if clinically indicated) for 4 weeks, and subsequently at approximately 4-week intervals, until resolution or stabilization of the event, whichever comes first. Appropriate clinical experts such as ophthalmologist, etc. should be consulted as deemed necessary.

All patients must be followed for safety for 30 days following the last dose of eltrombopag. In the case of patients who discontinue prematurely eltrombopag because efficacy but continue in the study (see [Section 6.1.2](#)) they will be followed for safety until complete all the planned visits of the study.

6.2.2.1 Management of hematologic side effects

Patients who experience a deep venous thrombosis (other than a line-related upper extremity thrombosis) or a pulmonary embolus, a transient ischemic attack or stroke, or a myocardial infarction at any time while on eltrombopag will discontinue eltrombopag.

6.2.2.2 Management of non-hematologic side effects

Patients who experience an infection requiring intravenous antibiotics will not discontinue eltrombopag. If the patient experiences infection severe enough to require intubation, eltrombopag will be withheld until the patient is more clinically stable.

6.2.3 Anticipated risks and safety concerns of the study drug

Thrombotic/Thromboembolic complications

The risk of thromboembolic events (TEEs) has been found to be increased in patients with chronic liver disease treated with 75 mg eltrombopag once daily for two weeks in preparation for invasive procedures. Six of 143 (4%) adult patients with chronic liver disease receiving eltrombopag experienced TEEs (all of the portal venous system) and two of 145 (1%) patients in the placebo group experienced TEEs (one in the portal venous system and one myocardial infarction). Five of the 6 patients treated with eltrombopag experienced the thrombotic complication at a platelet count $>200 \times 10^9/L$ and within 30 days of the last dose of eltrombopag. Eltrombopag is not indicated for the treatment of thrombocytopenia in patients with chronic liver disease in preparation for invasive procedures. In eltrombopag clinical trials in ITP, TEEs were observed at low and normal platelet counts. Caution should be used when administering eltrombopag to patients with known risk factors for thromboembolism including but not limited to inherited (e.g. Factor V Leiden) or acquired risk factors (e.g. ATIII deficiency, antiphospholipid syndrome), patients with prolonged periods of immobilization, malignancies, contraceptives and hormone replacement therapy, surgery/trauma, obesity and smoking. Platelet counts should be closely monitored and dose modifications must be made in accordance with parameters provided in the protocol.

The risks of thromboembolism and any of the following complications versus the benefit of improved platelet counts must be evaluated by the Investigator for each patient with known risks of TEEs.

Risk of hepatotoxicity

Eltrombopag administration can cause hepatobiliary laboratory abnormalities, severe hepatotoxicity and potentially fatal liver injury. In the controlled clinical studies in chronic ITP with eltrombopag, increases in serum ALT, AST and bilirubin were observed. Hepatotoxicity should be monitored and eltrombopag should be discontinued if hepatobiliary abnormalities are observed as described in [section 6.2.1.2](#). Exercise caution when administering eltrombopag to patients with hepatic disease.

Ophthalmic changes

Cataracts were observed in toxicology studies of eltrombopag in rodents but have not been reported at significant rates over control groups in human trials. In controlled studies in thrombocytopenic patients with HCV receiving interferon therapy (n = 1439), progression of pre-existing baseline cataract(s) or incident cataracts was reported in 8% of the eltrombopag group and 5% of the placebo group. Retinal hemorrhages, mostly grade 1 or 2, have been reported in HCV patients receiving interferon, ribavirin and eltrombopag (2% of the eltrombopag group and 2% of the placebo group). Hemorrhages occurred on the surface of the retina (preretinal), under the retina (subretinal), or within the retinal tissue. Ophthalmological examination (see [Section 7.3.2.8](#)[7.3.2.8](#)) should be performed at baseline, 24 weeks, and also at Final Visit (or Early Withdrawal). Eltrombopag continuation should be re-considered if suspected cataract development or worsening, or in case of retinal hemorrhages. In clinical trials of eltrombopag in SAA cataracts have not been reported. There is no evidence of cataracts in PGF.

Bone marrow reticulin formation and risk of bone marrow fibrosis

Eltrombopag may increase the risk for development or progression of reticulin fibers within the bone marrow. The relevance of this finding, as with other TPO-R agonists, has not been established yet.

If immature or dysplastic cells not linked to primary disease are observed, peripheral blood smears should be examined for new or worsening morphological abnormalities (e.g., teardrop and nucleated red blood cells, immature white blood cells) or cytopenia(s). If the patient develops new or worsening morphological abnormalities and cytopenia(s) not linked to primary disease, treatment with eltrombopag should be discontinued. A bone marrow biopsy must be considered, including staining for fibrosis.

Progression of existing myelodysplastic syndrome

TPO-R agonists are growth factors that lead to thrombopoietic progenitor cell expansion, differentiation and platelet production. The TPO-R is predominantly expressed on the surface of cells of the myeloid lineage. For this class of TPO-R agonists, there is a concern that they may stimulate the progression of existing hematopoietic malignancies such as myelodysplastic syndrome.

In clinical studies with a TPO-R agonist, romiplostim and eltrombopag, in patients with MDS, cases of transient increases in blast cell counts were observed and cases of MDS disease progression to AML were reported.

In the CETB115AUS01T study, eltrombopag in combination with IST was assessed in patients with SAA. Published results indicate that clonal cytogenetic evolution with dysplastic changes occurred at a similar frequency compared to NIH historic experience with standard IST (10-15%) (Townsley et al., 2017). All patients should be monitored regularly for new or worsening morphological abnormalities or cytopenia(s), and may require bone marrow evaluation, as clinically indicated.

Eltrombopag should be discontinued in case of suspected myeloproliferation not linked to the primary disease or if there is a suspected myeloproliferation due to eltrombopag treatment.

Bleeding events after study drug discontinuation

Following discontinuation of eltrombopag, platelet counts return to baseline levels within 2 weeks in the majority of patients, which increases the bleeding risk and, in some cases, may lead to bleeding. Platelet counts should be monitored as per protocol following discontinuation of eltrombopag.

6.2.4 Follow-up on potential drug-induced liver injury (DILI) cases

Patients with transaminase increase combined with TBIL increase may be indicative of potential DILI and should be considered as clinically important events.

The threshold for potential DILI may depend on the patient's baseline AST/ALT and TBIL value; patients meeting any of the following criteria will require further follow-up as outlined below:

- For patients with normal ALT and AST and TBIL values at baseline: AST or ALT $>3.0 \times$ ULN combined with TBIL $>2.0 \times$ ULN.
- For patients with elevated AST or ALT or TBIL value at baseline: [AST or ALT $>2.0 \times$ baseline AND $>3.0 \times$ ULN] **OR** [AST or ALT $>8.0 \times$ ULN], combined with [TBIL $>2.0 \times$ baseline AND $>2.0 \times$ ULN].

Medical review needs to ensure that liver test elevations are not caused by cholestasis, defined as alkaline phosphatase (ALP) elevation $>2.0 \times$ ULN with R value <2 in patients without bone metastasis, or elevation of ALP liver fraction in patients with bone metastasis.

NOTE: The R value is calculated by dividing the ALT by the ALP, using multiples of the ULN for both values. It denotes whether the relative pattern of ALT and/or ALP elevation is due to cholestatic (R ≤ 2), hepatocellular (R ≥ 5), or mixed (R >2 and <5) liver injury.

In the absence of cholestasis, these patients should be immediately discontinued from study drug treatment, and repeat LFT testing as soon as possible, preferably within 48 hours from the awareness of the abnormal results.

The evaluation should include laboratory tests, detailed history, physical assessment and the possibility of liver metastasis or new liver lesions, obstructions/compressions, etc.:

1. Laboratory tests should include: ALT, AST, albumin, creatine kinase, total bilirubin, direct and indirect bilirubin, GGT, prothrombin time (PT)/INR and alkaline phosphatase.

2. A detailed history, including relevant information, such as review of ethanol, concomitant medications, herbal remedies, supplement consumption, history of any pre-existing liver conditions or risk factors, should be collected.
3. Further testing for acute hepatitis A, B, C or E infection and liver imaging (e.g. biliary tract) may be warranted.
4. Obtain PK sample, as close as possible to last dose of study drug, if PK analysis is performed in the study.
5. Additional testing for other hepatotropic viral infection (CMV, EBV or HSV), autoimmune hepatitis or liver biopsy may be considered as clinically indicated or after consultation with specialist/hepatologist.

All cases confirmed on repeat testing meeting the laboratory criteria defined above, with no other alternative cause for LFT abnormalities identified should be considered as “medically significant”; thus, they meet the definition of SAE ([Section 8.2.1](#)) and should be reported as SAE using the term “potential drug-induced liver injury”.

All events should be followed up with the outcome clearly documented.

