Isolated AST or ALT elevation	
> ULN - 3.0 x ULN	Maintain dose level
> 3.0 - 5.0 x ULN	
Maintain dose level.
 
Repeat LFTs^b as soon as possible, preferably within 48-72 hours from awareness of the abnormal results.
 
If abnormal lab values are confirmed upon the repeat test, then monitor LFTs^b weekly, or more frequently if clinically indicated, until resolved to $\leq 3.0 \times$ ULN
 
Discontinue patient from the study treatment if elevation is combined with any of the following:
 
 • Clinical symptoms of liver injury or evidence for hepatic decompensation • Progressively increasing LFTs^b upon repeat testing • Persistence for ≥ 4 weeks

> 5.0 - 10.0 x ULN	Mandatory: Interrupt dose. Repeat LFTs ^b as soon as possible; preferably within 48-72 hours from awareness of the abnormal results. Monitor LFTs ^b weekly, or more frequently if clinically indicated until resolved to $\leq 3.0 \times$ ULN then: If resolved in ≤ 14 days, maintain dose level If resolved > 14 days, decrease one dose level ^e
> 10.0 - 20.0 x ULN	Mandatory: Interrupt dose. Repeat LFTs ^b as soon as possible, preferably within 48-72 hours from awareness of the abnormal results. Monitor LFTs ^b weekly, or more frequently if clinically indicated until resolved to \leq baseline. Then decrease one dose level ^e .
> 20.0 x ULN	Mandatory: Discontinue patient from study drug treatment. Repeat LFTs ^b as soon as possible, preferably within 48-72 hours from awareness of the abnormal results. Monitor LFTs ^b weekly, or more frequently if clinically indicated until resolved to \leq baseline or stabilization over 4 weeks.
Combined^c elevations of AST or ALT and total bilirubin	
For patients with normal baseline ALT and AST and total bilirubin value, [AST or ALT $> 3.0 \times$ ULN] combined with [total bilirubin $> 2.0 \times$ ULN] without evidence of cholestasis ^d OR For patients with elevated baseline AST or ALT [AST or ALT $> 3 \times$ baseline] OR [AST or ALT $> 5.0 \times$ ULN], whichever is lower, combined with [total bilirubin $> 2 \times$ baseline AND $> 2.0 \times$ ULN]	Mandatory: Permanently discontinue patient from study drug treatment. Repeat as soon as possible, preferably within 48 hours from awareness of the abnormal results, then with weekly monitoring of LFTs ^b), or more frequently if clinically indicated, until AST, ALT, or bilirubin have resolved to baseline or stabilization over 4 weeks.

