
All dose modifications should be based on the worst preceding toxicity.
 
^a Common Toxicity Criteria for Adverse Events (CTCAE Version 4.03)
 
^b Core LFTs consist of ALT, AST, GGT, total bilirubin (fractionated [direct and indirect], if total bilirubin $> 2.0 \times$ ULN), and alkaline phosphatase (fractionated [quantification of isoforms], if alkaline phosphatase $> 2.0 \times$ ULN.)
 
^c "Combined" defined as total bilirubin increase to the defined threshold concurrently with ALT/AST increase to the defined threshold
 
If combined elevations of AST or ALT and total bilirubin do not meet the defined thresholds, please follow the instructions for isolated elevation of total bilirubin and isolated elevation of AST/ALT, and take a conservative action based on the degree of the elevations (e.g. discontinue treatment at the situation when omit dose is needed for one parameter and discontinue treatment is required for another parameter). After all elevations resolve to the defined thresholds that allow treatment re-initiation, re-start the treatment either at the same dose or at one dose lower if criterion for dose reduction is met.
 
^d "Cholestasis" defined as ALP elevation ($> 2.0 \times$ULN and R value < 2) in patients without bone metastasis, or elevation of ALP liver fraction in patients with bone metastasis. The R value is calculated by dividing the ALT by the ALP, using multiples of the ULN for both values. It denotes whether the relative pattern of ALT and/or ALP elevation is due to cholestatic (R ≤ 2), hepatocellular (R ≥ 5), or mixed (R > 2 and < 5) liver injury.
 
^e "One dose level" defined as eltrombopag dose reduction by 25 mg.
	

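### For patients with raised baseline AST or ALT, Table 6-3 and section 6.2.4 set different enzyme limits for stopping eltrombopag, and the protocol does not say which governs.

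*Protocol*

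**What the plan says.** **Table 6-3 (section 6.2.1.2), combined elevations.** The row beginning "For patients with elevated baseline AST or ALT" applies when AST or ALT exceeds the lower of 3 x baseline and 5 x ULN, and total bilirubin exceeds both 2 x baseline and 2 x ULN. The action is "Permanently discontinue patient from study drug treatment". The row for patients with normal baseline values exempts cholestasis; this row does not.

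**Table 6-3, footnote c.** If the combined thresholds are not met, "please follow the instructions for isolated elevation of total bilirubin and isolated elevation of AST/ALT". The footnote also asks for conservative action according to the degree of the elevations. Once all elevations have resolved to the levels that permit treatment, it says to "re-start the treatment either at the same dose or at one dose lower if criterion for dose reduction is met".

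**Table 6-3, isolated rows.** For AST or ALT above 3 and up to 5 x ULN, the dose is maintained and tests are repeated. There is one qualification: "Discontinue patient from the study treatment if elevation is combined with any of the following", namely signs of liver injury or decompensation, a progressive rise, or persistence for 4 weeks or more. For bilirubin above 1.5 and up to 3 x ULN, dosing is interrupted until bilirubin is at or below 1.5 x ULN. It then resumes at the same dose (within 14 days) or 25 mg lower (later). If a rise in that range is purely indirect, no dose change is required.

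**Section 6.2.4.** "For patients with elevated AST or ALT or TBIL value at baseline", the limit is AST or ALT above both 2 x baseline and 3 x ULN, or above 8 x ULN, with the same bilirubin condition. Absent cholestasis, "these patients should be immediately discontinued from study drug treatment". A work-up follows. The SAE rule covers "All cases confirmed on repeat testing meeting the laboratory criteria defined above" when no other cause is found.

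**Eligibility (section 5.2).** Exclusion 11 admits AST and ALT up to 3 x ULN. Exclusion 13 admits total bilirubin below 1.5 x ULN.

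**The concern.** Both rules are current text, both order discontinuation, and neither refers to the other. Section 6.2.3 points sites to section 6.2.1.2 only. Below the Table 6-3 combined limit, footnote c leads to the isolated rows and their restart rules, not to section 6.2.4. The same laboratory result can therefore mean discontinuation under one section and an interruption with restart, or no dose change, under the other.

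The protocol itself warns that the drug can cause liver injury that may be fatal. A site working from Table 6-3 may restart a patient whom section 6.2.4 discontinues. A site working from section 6.2.4 may not open the work-up, or consider the SAE report, for a patient whom Table 6-3 stops permanently. SAP section 9 tabulates seriousness and action taken for each adverse event, so similar liver cases could be counted differently.

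**Working it through.** **Inputs.** Let b be the baseline of the raised enzyme in x ULN, so 1 < b <= 3 (exclusion 11). Take the shared bilirubin condition as met. Its limit is the larger of 2 x baseline and 2 x ULN. With baseline bilirubin below 1.5 x ULN, that is 2.0 to just under 3.0 x ULN.

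**Formulas.** Table 6-3: T = min(3b, 5). Section 6.2.4: D = min(max(2b, 3), 8). As 2b is at most 6, the 8 x ULN arm never binds here.

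| b | T (Table 6-3) | D (6.2.4) | T - D |
|---|---|---|---|
| 1.2 | 3.6 | 3.0 | 0.6 |
| 1.5 | 4.5 | 3.0 | 1.5 |
| 1.67 | 5.0 | 3.33 | 1.67 (widest) |
| 2.0 | 5.0 | 4.0 | 1.0 |
| 2.5 | 5.0 | 5.0 | 0 |
| 2.75 | 5.0 | 5.5 | -0.5 |
| 3.0 | 5.0 | 6.0 | -1.0 |

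For patients with all baseline values normal, both texts use AST or ALT above 3 x ULN with bilirubin above 2 x ULN. The mismatch is confined to abnormal baselines.

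**1 < b < 2.5: section 6.2.4 is met first (absent cholestasis).** The disputed enzyme values, above D and up to T, always lie in the isolated row for more than 3 and up to 5 x ULN. Example: baseline ALT 1.5, bilirubin 0.8; on treatment ALT 4.0, bilirubin 2.5, no cholestasis.
- Section 6.2.4: 4.0 > max(3.0, 3) and 2.5 > max(1.6, 2), so discontinue.
- Table 6-3: 4.0 < 4.5, so the combined row is unmet. The ALT row maintains the dose unless one of its qualifying features is present. The bilirubin row interrupts, with restart once all elevations have resolved.
- If the bilirubin rise is indirect only, the bilirubin row requires no dose change either.

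**2.5 < b <= 3: Table 6-3 is met first.** Example: baseline ALT 3.0, on treatment 5.5, same bilirubin values. Table 6-3 stops permanently (5.5 > 5.0). Section 6.2.4 is not met (5.5 < 6.0), so its work-up and SAE rule are not triggered.

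**Only bilirubin raised at baseline.** Section 6.2.4 covers this patient; neither combined row of Table 6-3 does. Example: baseline ALT 0.8, bilirubin 1.2; on treatment ALT 12, bilirubin 2.5, no cholestasis. Section 6.2.4: 12 > 8 and 2.5 > max(2.4, 2), so discontinue. The isolated rows of Table 6-3 interrupt and then, after resolution, restart 25 mg lower.

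**Cholestasis.** Example: baseline ALT 1.5, bilirubin 0.8; on treatment ALT 4.8, ALP 3, bilirubin 2.5. R = 4.8/3 = 1.6, below 2, with ALP above 2 x ULN, so this is cholestasis by the protocol's definition. Table 6-3 stops permanently (4.8 > 4.5); section 6.2.4 exempts the patient.

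**The case against.** The best defence is that both sections bind, so a careful site stops when either is met. Footnote c also asks for conservative action, and the bilirubin row normally interrupts dosing anyway. A patient stopped under Table 6-3 alone still has prompt repeat testing and weekly liver tests. Section 6.2.2 adds toxicity follow-up, hepatobiliary events are of special interest under section 8.1.3, and medically significant events remain SAEs under section 8.2.1.

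Most of this stands, and it limits the harm. It does not remove the conflict. Footnote c's example of conservative action picks the stricter of the two isolated rows. It does not bring in section 6.2.4, and the footnote then gives a restart path. No sentence tells the site to apply whichever section is stricter.

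Three stronger readings should be resisted.
- A reader might infer that Table 6-3 generally keeps the drug going where section 6.2.4 stops it. It usually interrupts; the clear exception is an indirect-only bilirubin rise. Nor does recovery of bilirubin alone permit restart: footnote c requires all elevations to resolve.
- A reader might apply Table 6-3's 3 x baseline to an enzyme that was normal at baseline because the other was raised. For an enzyme starting at 0.3 x ULN that would mean a permanent stop above 0.9 x ULN, inside the normal range. The row addresses raised baselines and does not sensibly support this.
- A reader might take discontinuation under section 6.2.4 as certainly permanent. The glossary points that way, but Table 6-2 and section 6.2.1.3 use the word for reversible stops, and section 6.2.4 does not bar restart.

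**Conclusion.** The inconsistency is real and should be fixed; its weight is modest. For one raised enzyme the two limits agree only at b = 2.5. Section 6.2.4 is stricter below that, by up to 1.67 x ULN, and Table 6-3 is stricter above it, by up to 1.0 x ULN. The practical differences are restart, the indirect-only exception, cholestasis, the missing combined row for bilirubin-only baseline elevation, and the start of the work-up and SAE rule.

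This assumes that baseline is the pre-treatment value meeting exclusions 11 and 13, and that multiples of baseline refer to the raised enzyme's own value. The documents give no rate of combined elevations, so no expected count can be stated; few of the 33 patients are likely to be involved. The primary endpoint and its analysis are unaffected.

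**What to change.** Add the following to the Table 6-3 combined row, to footnote c and to section 6.2.4:

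*Permanently discontinue eltrombopag and start the section 6.2.4 work-up when either the Table 6-3 combined criterion or the section 6.2.4 criterion (absent cholestasis) is met. The isolated rows and their restart rules apply only when neither is met. Multiples of baseline in Table 6-3 apply to an enzyme that was above ULN at baseline; for an enzyme normal at baseline the limit is more than 3 x ULN.*

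State also that confirmed cases meeting either criterion, with no alternative cause, are reported under the SAE rule of section 6.2.4.

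This keeps the stricter limit for a raised enzyme and covers bilirubin-only baseline elevation through section 6.2.4. It also keeps Table 6-3's stop in cholestatic patients with raised baseline enzymes, which the sponsor should confirm is intended. Making the section 6.2.4 stop permanent is a clinical choice; it matches Table 6-3.

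Cost: a short protocol amendment and a site memo, with no new data. A few patients who might have restarted would stop for good, and a few more would have the work-up.

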6.3 Concomitant medications

The patient must be told to notify the investigational site about any new medications he/she takes after the start of the study drug. All medications (other than study drug) and significant non-drug therapies (including physical therapy, herbal/natural medications and blood transfusions) administered during the study, and those taken 30 days prior to study entry must be listed on the Concomitant Medications CRF.

